2.9.3. Vital Signs

Individual vital sign measurements (systolic/diastolic BP and heart rate) will be listed by measurement time and summarized using descriptive statistics. Individual change from baseline in vital sign measurements will be calculated and summarized descriptively. A clinically significant change from baseline may be recorded as an AE if deemed appropriate by the PI or sponsor.

2.9.4. Electrocardiogram

EGC results will be summarized for each visit at which it is performed. Any clinically significant change from baseline may be recorded as an AE if deemed appropriate by the PI or sponsor. Individual ECG values will be listed by visit and summarized using descriptive statistics. Intervals to be provided for each ECG are: RR, PR, QRS, QT, and QTcF.

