2.10 Schedule of Events

[Table 1](#) below describes the schedule of events for all study visits.

Table 1. Schedule of Events for All Study Visits

Visit	Screening	Randomization /Baseline	Visit 1 TC	Visit 2	Visit 3	Visit 4	Visit 5	Early Term
Days	-7 ± 2 days	0	7(-5/+2)	28(-5/+2)	56(-5/+2)	84(-5/+2)	168 ± 5	
Informed Consent	X							
Medical History	X							
Demographics	X							
Inclusion/Exclusion Criteria	X							
Mini Mental State Exam	X							
4-Meter Walk Test	X							
Concomitant Medications	X	X	X	X	X	X	X	X
Physical Exam ¹	X			X		X	X	X
Vital Signs	X	X		X	X	X	X	X
ECG ²	X	X ²				X ²	X	X
Hematology/Chemistry/Urinalysis ^{12,13}	X ¹²	X		X	X ¹³	X	X ¹³	X
Lipid Profile		X		X		X	X	X
Coagulation		X		X		X	X	X
Thyroid Markers ³		X				X		X
Vitamin D		X				X		X
Bone Turnover Markers ⁴		X		X	X	X	X	X
Pituitary/Adrenal Hormone Blood Tests ⁵		X		X		X		X
PSA (males)	X					X		X
Pancreatic Endocrine Markers ⁶		X		X	X	X		X
DXA Scan		X				X	X	X
Physical Performance Assessments ⁷		X		X	X	X	X	X
Patient Reported Outcomes ⁸	X (pre-Fx. Only)	X		X	X	X	X	X
Plasma Concentration Blood Samples ⁹				X ⁹	X ⁹	X ⁹	X ⁹	
Diary Card ¹⁰		X		X	X	X		
IP Administration/Dispensation/Compliance ¹¹		X	X	X	X	X		X
Averse Events		X	X	X	X	X	X	X
Study Disposition							X	X

¹ Height and weight will be measured at Screening. Weight only at Visits 2, 4, and 5.

² At Randomization and at Visit 4, the ECG will occur at 2 hours post-dose.

³T3, T4, TSH

⁴ s-CTX and s-PINP

⁵ The hormones tested will include follicle stimulating hormone (FSH), luteinizing hormone (LH), sex-hormone binding globulin (SHBG), estradiol, cortisol, aldosterone, adrenocorticotrophic hormone (ACTH) and total and free testosterone.

⁶ Endocrine pancreatic markers include fasting insulin and fasting glucagon

⁷ 6MWT and BORG Scale, Grip Strength, and SPPB.

⁸ Pre-fracture PADLs/IADLs at Screening. SF-36 and post-fracture PADLs/IADLs at Randomization. Post-fracture PADLs/IADLs only at Visits 2 and 3. SF-36 and post-fracture PADLs/IADLs at Visits 4 and 5 and Early Termination.

⁹Samples will be drawn pre-dose and at 2 hours (± 10 min) post-dose at Visits 2, 3, and 4. Visit 5 sample may be drawn along with the other blood work samples.

¹⁰ Diary cards provided at Randomization and Visit 3, reviewed at Visits 2 and 4.

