16. ECG will be performed at Screening. Subjects with QTcF interval >450 msec (or >500 msec in the presence of a bundle branch block or paced ventricular rhythm) or any other exclusionary cardiac conditions noted previously on the locally read ECG are excluded from study participation. Other abnormal findings on the ECG should be carefully considered and any subject excluded who, in the judgment of the PI, may not safely complete treatment in this study.
17. History of active or uncontrolled heart failure or hypertension within 3 months of Screening.
18. Symptoms of acute or unstable coronary artery disease within 6 months of Screening.
19. History of cerebrovascular disease within 1 year of Screening.
20. History of epilepsy or any other seizure disorder within 1 year of Screening.
21. History of unexplained or untreated syncope in the past 12 months.
22. History of organ transplantation.
23. Positive history of human immunodeficiency virus, or acute/active hepatitis B, or hepatitis C.
24. Malignancy within 5 years of Screening (with the exception of previously treated basal cell carcinoma and squamous cell skin carcinoma in-situ).
25. History (within 2 years prior to Screening) of alcohol or drug/solvent abuse.
26. Documented sensitivity to any of the ingredients in the Investigational Product (IP) formulation.

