4.3 Removal of Subjects from Therapy or Assessment

Subjects are free to withdraw consent and discontinue participation in the study at any time, without prejudice to further treatment. Subjects who discontinue prior to day 28 will be replaced.

A subject's participation in the study may be discontinued at any time at the discretion of the investigator. The following are reasons that may lead to a subject's discontinuation:

1. Subject develops intolerable adverse effects.
2. Subjects who experience a >60 msec prolongation of QTc interval or absolute QTc >500 msec (or >550 msec in the presence of a bundle branch block or paced ventricular rhythm) will be discontinued from treatment and followed by ECG until the QTc returns to baseline levels. Other abnormal findings on the ECG should be carefully considered and any subject excluded who, in the judgment of the PI, may not safely complete treatment in this study will be terminated from participation.
3. The subject is grossly non-compliant defined as:
 - a. Uncooperative/noncompliant and will not adhere to study responsibilities, including failure to appear at two consecutive visits.

- b. Taking prohibited medications as described in [Section 5.7.1](#), pending evaluation by the Sponsor.
- 4. The subject's health would be jeopardized by continued participation.
- 5. In the opinion of the Investigator, it is in the best interest to discontinue subject from study.
- 6. The subject wishes to withdraw for any reason.
- 7. The Sponsor elects to end the study, or any portion thereof, for any reason.
- 8. Any other safety results or adverse experiences that, in the opinion of the investigator, raise concerns about the safety or tolerability of VK5211.

Although a subject will not be obliged to give his/her reason for withdrawing prematurely, the Investigator will make a reasonable effort to obtain the reason while fully respecting the subject's rights. All subjects who are randomized and treated (i.e., received any amount of study drug) will be included in the safety analyses. Thus, every effort will be made to contact any subject who fails to attend any follow-up appointments/contacts, in order to ensure that he/she is in satisfactory health.

If a subject withdraws from the study as a result of meeting discontinuation criteria after the start of study drug administration, all post-treatment evaluations must be completed.

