9.5 Safety Evaluation

All safety variables (including adverse experiences, vital signs measurements, clinical laboratory results, ECG results, and other safety variables) will be listed by subject and domain. The incidence of all AEs, treatment-emergent adverse experiences, and treatment-related adverse experiences will be tabulated by MedDRA® preferred term, system organ class, dose, and treatment group. All laboratory results, vital sign measurements, and other safety variables will be summarized using appropriate descriptive statistics. The incidence of treatment emergent abnormalities will be summarized by dose.

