2.9.2. Safety Laboratory Evaluations

Individual laboratory values will be listed by visit and summarized using descriptive statistics. Individual change from baseline in laboratory values will be calculated and summarized descriptively. Shift tables from baseline to final visit will also be produced for the laboratory

assessments based on the categories of Low, Normal, and High. Selected lab parameters will be summarized by CTC grade. A clinically significant change from baseline may be recorded as an AE if deemed appropriate by the PI or sponsor.

To better view the results of the liver function tests, the liver function tests will be presented in a separate table.

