14.2.18.2.3	Summary of Whole Body Dual Energy X-Ray Absorptiometry (DXA) scan – Appendicular Lean Body Mass – Site Results with DXA Type Correction Factor – Sex Effect - Stringent Definition of Valid DXA - Per Protocol Population
14.2.18.2.4	Summary of Whole Body Dual Energy X-Ray Absorptiometry (DXA) scan – Appendicular Lean Body Mass – Site Results with DXA Type Correction Factor - Liberal Definition of Valid DXA - Per Protocol Population

Table Number	Table Title
14.2.18.2.5	Summary of Whole Body Dual Energy X-Ray Absorptiometry (DXA) scan – Appendicular Lean Body Mass – Site Results with DXA Type Correction Factor – Multiple Imputation Method - Liberal Definition of Valid DXA - Per Protocol Population
14.2.18.2.6	Summary of Whole Body Dual Energy X-Ray Absorptiometry (DXA) scan – Appendicular Lean Body Mass – Site Results with DXA Type Correction Factor – Sex Effect - Liberal Definition of Valid DXA - Per Protocol Population
14.3.1.1.1	Summary of Adverse Events – Safety Population
14.3.1.1.2	Summary of Treatment Emergent Adverse Events by System Organ Class and Preferred Term – Safety Population
14.3.1.1.3	Summary of Treatment Emergent Adverse Events in Decreasing Order of Frequency by Preferred Term – Safety Population
14.3.1.1.4	Summary of Treatment Emergent Adverse Events by Severity – Safety Population
14.3.2.1	Summary of Treatment Emergent Adverse Events Leading to Discontinuation by System Organ Class and Preferred Term – Safety Population
14.3.2.2.1	Summary of Serious Adverse Events by System Organ Class and Preferred Term – Safety Population
14.3.2.2.2	Summary of Serious Adverse Events in Decreasing Order of Frequency by Preferred Term – Safety Population
14.3.3.1	Summary of Liver Function Tests – Safety Population
14.3.3.2	Summary of Safety Lab Parameters – Hematology – Safety Population
14.3.3.3	Summary of Safety Lab Parameters – Chemistry – Safety Population
14.3.3.4	Summary of Safety Lab Parameters – Urinalysis – Safety Population
14.3.4.1	Shifts in Liver Function Tests – Safety Population
14.3.4.2	Shifts in Selected Lab Parameters by CTC Grade – Safety Population
14.3.4.3	Shifts in Safety Lab Parameters – Hematology – Safety Population
14.3.4.4	Shifts in Safety Lab Parameters – Chemistry – Safety Population
14.3.5	Summary of Vital Signs – Safety Population
14.3.6	Summary of Electrocardiogram Results – Safety Population
14.3.7	Summary of Physical Exam Findings – Safety Population

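### SAP 2.9.4 plans no change-from-baseline summary for ECG, so a within-subject QTc rise above 60 msec, one of the protocol's two stopping limits, need not show in the planned summaries

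*SAP*

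**What the plan says.** The SAP treats three kinds of safety measurement in neighbouring sections.

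- Laboratory tests (SAP 2.9.2): "Individual change from baseline in laboratory values will be calculated and summarized descriptively". Shift tables are also planned.
- Vital signs (SAP 2.9.3): "Individual change from baseline in vital sign measurements will be calculated and summarized descriptively".
- ECG (SAP 2.9.4): "Individual ECG values will be listed by visit and summarized using descriptive statistics". The intervals are RR, PR, QRS, QT and QTcF. Change from baseline appears only as something that may be recorded as an adverse event at the discretion of the investigator or sponsor.

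Protocol 9.5.4 plans the same ECG summaries as SAP 2.9.4. The one ECG table named in SAP 4.1 is 14.3.6, "Summary of Electrocardiogram Results – Safety Population". The named shift tables, 14.3.4.1 to 14.3.4.4, are all for laboratory data.

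Protocol 4.3 sets the QTc limits for stopping treatment: "Subjects who experience a >60 msec prolongation of QTc interval or absolute QTc >500 msec". The absolute limit becomes 550 msec with bundle branch block or a paced rhythm. Protocol 4.2 excludes at entry "Subjects with QTcF interval >450 msec (or >500 msec in the presence of a bundle branch block or paced ventricular rhythm"). Footnote 2 of Table 1 in Protocol 2.10 fixes the timing: "At Randomization and at Visit 4, the ECG will occur at 2 hours post-dose". SAP 2.3 defines baseline, in general, as the last observation before the first dose.

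**The concern.** Comparing 12-lead ECG data with placebo is part of a secondary objective (Protocol 3.2, SAP 1.3.2). The protocol treats a QTc rise above 60 msec as serious enough to stop treatment. That quantity is a difference between two readings in the same person. The SAP plans summaries of the readings at each visit and does not plan a summary of the difference, although it does so for laboratory tests and vital signs.

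If the SAP is followed as written, the report need not say how many subjects in each arm had such a rise. A reader would have to work it out from the individual listing. A statement that no subject in any arm reached the limit would likewise have no planned table behind it.

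**Working it through.** The plan gives no figure to reproduce here. The check is textual, with a little arithmetic.

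**1. Which ECG is the baseline?** Table 1 schedules ECGs at Screening, Randomization, Visit 4, Visit 5 and Early Termination. The Randomization ECG is taken 2 hours after the first dose. Screening is therefore the only scheduled pre-dose ECG and is the baseline under SAP 2.3. SAP 2.9.4 does not say so.

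**2. Can a by-visit maximum show a rise above 60 msec?** Not in general. Two subjects can share the same maximum:

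- 450 + 20 = 470 msec, a rise of 20 msec
- 405 + 65 = 470 msec, a rise of 65 msec

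The range that the maximum can miss follows from the two limits. For a subject without bundle branch block or pacing, a rise above 60 msec forces QTcF above 500 msec only if entry QTcF is at least 500 − 60 = 440 msec. The entry cap is 450 msec. So only entry values from 440 to 450 msec guarantee that the maximum reveals the rise. Below 440 msec it need not. From 405 msec, for example, any rise above 60 and up to 500 − 405 = 95 msec stays at or below 500 msec.

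**3. Can a by-visit mean show it?** SAP 2.14 expects about 23 subjects per arm to complete. One subject rising 61 msec shifts the arm mean by 61 / 23 = 2.65, or about 2.7 msec. A mean cannot tell one large rise from a small shift across the arm. The SD may widen, but it does not separate a rise from ordinary spread between subjects.

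**4. Where does the gap bite?** Visit 4 is the only scheduled on-treatment ECG after repeated dosing for subjects who complete treatment. The Randomization ECG follows a single dose, and Visit 5 comes about 12 weeks after treatment ends. At Visit 4 the dose is given in clinic, the ECG follows 2 hours later, and no further drug is dispensed (Table 1, footnotes 2 and 11). A crossing there cannot lead to a treatment stop, so it need not appear as a discontinuation.

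**5. Do the general clauses fill the gap?** Protocol 9.5 includes ECG results among the safety variables and states: "The incidence of treatment emergent abnormalities will be summarized by dose". It gives no QTc criterion, and the SAP does not take the commitment up for ECG. SAP 2.1 allows derived parameters to be tabulated where appropriate, but names no ECG change.

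**The case against.** The strongest case against is that most of what matters can be recovered elsewhere.

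- **Absolute limit.** SAP 2.1 plans maxima by treatment group. If an arm's maximum is at or below 500 msec, nobody in that arm exceeded 500 msec at that scheduled visit. This stands. A reader might infer that both QTc limits go unreported; the documents do not support that, and the concern rests on the change limit.
- **Individual data.** Listing 16.2.9.2 gives the ECG values, sorted by treatment and subject (SAP 3.2). With about 23 completers per arm, subtracting Screening from Visit 4 is easy. This stands: no information is lost, only a planned summary is missing.
- **Adverse event routes.** A crossing that leads to discontinuation, or needs further diagnostic testing, meets the adverse event criteria in Protocol 10.2. An independent committee also reviews unblinded safety data (Protocol 10.1). This stands in part. At Visit 4 no treatment stop is possible. Protocol 10.2 also says that merely repeating a test, or a finding the investigator judges not clinically significant, is not an adverse event.
- **Unseen shells.** SAP 4.3 keeps the table shells in a separate file. A reader might infer from its title that Table 14.3.6 has no change columns. That does not follow: the vital signs table, 14.3.5, has an equally general title although SAP 2.9.3 plans change from baseline. The point is confined to what the SAP text requires.
- **No broken promise.** Protocol 9.5.4 and SAP 2.9.4 agree, so the SAP has not dropped a specific ECG commitment. This also stands. It makes the change an improvement to the plan rather than the repair of a contradiction.

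**Conclusion.** The point holds as a minor one. As written, SAP 2.9.4 does not require the change from baseline that SAP 2.9.2 and 2.9.3 require for laboratory tests and vital signs. The summaries it does require need not reveal a QTcF rise above 60 msec when entry QTcF is below 440 msec. Visit 4 is where this matters most.

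The only size the documents support is that one subject rising 61 msec moves the mean of a 23-subject arm by about 2.7 msec. This rests on the completer number in SAP 2.14. A reader might want to go further and ask how many such subjects would be needed before the arm stood apart from placebo. The documents give no SD for QTcF and plan no between-arm interval for ECG, so no such number is offered.

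Nor do the documents suggest that a QTc problem is expected. The Introduction describes ECG values in the study of older subjects as unremarkable, and Protocol 5.3 reports no clinically important ECG changes in the healthy-volunteer studies. The true count of rises above 60 msec may be zero.

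**What to change.** In SAP 2.9.4 and Table 14.3.6:

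1. State that the Screening ECG is the ECG baseline, because the Day 0 ECG is post-dose.
2. Summarize by arm the change from Screening in QTcF and the other intervals at Day 0 (2 hours post-dose), Visit 4 and Visit 5, with Early Termination ECGs placed by the Day 112 rule in SAP 2.16.
3. Add n (%) by arm with any post-dose QTcF increase above 60 msec and with any post-dose QTcF above 500 msec. Include unscheduled ECGs, since SAP 2.16 plans descriptive statistics only for planned visits.
4. Name QTcF as the correction, since Protocol 4.3 says only QTc.
5. Apply the 550 msec limit only where bundle branch block or a paced rhythm is recorded. The documents do not show that this is captured as a field at each ECG.

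The cost is a few sentences and some extra rows in an existing table. The interval values are already collected, and the primary analysis is not affected.

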2.9.5. Physical Examination

Physical examination results will be summarized for each visit at which it is performed.

2.10. Efficacy Evaluations

Efficacy assessments will be listed in data listings, and summarized in tables. Figures will be generated for selected efficacy evaluations to better understand the results.

2.10.1. Primary Efficacy Assessment

The absolute and percentage change in total body less head lean body mass at Visit 4 (Month 3) will be analyzed using an Analysis of Covariance model with baseline value as a covariate and treatment and region (country) as factors.

Observed values, percentage change and absolute change from baseline for all available visits will be summarized using mean, standard deviation, coefficient of variation (CV%), median, minimum and maximum. A 95% confidence interval on the placebo adjusted change from baseline will also be presented.

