7 STUDY ACTIVITIES

7.1 Screening Visit (Day -7± 2)

At the initial Screening, potential subjects will be given a detailed presentation describing the nature, purpose, risks, and requirements of the study and will also receive detailed written information.

They will have adequate opportunity to ask the appropriate person of the clinical staff (i.e., Principal Investigator or designee) presenting the study about any aspect of the study. Once the subject is satisfied that he/she is willing to participate in the study, he/she will be asked to sign the study ICF. The ICF will include all the elements as outlined in Section 4.8.10 of the ICH guidelines for GCP (E6). The clinical personnel obtaining written consent from the subject will also sign the form to confirm consent has been obtained.

Once signed, the Investigator will retain the original for the subject's study records and provide the subject with a signed copy. The Investigator will verify that informed consent has been obtained from each subject prior to admission into the study and prior to the subject undergoing any study-related procedures.

Within 3-11 weeks post-fracture, all screening activities subsequent to obtaining informed consent will be conducted and consist of the following:

- Satisfaction of inclusion/exclusion criteria ([Section 4](#))
- Completion of medical and social history including tobacco, alcohol, and caffeine use
- Concomitant medications assessment
- Collection of demographic data (sex, age, race/ethnicity)
- Mini Mental State Exam (MMSE)
- Physical examination, including height and weight
- 4-Meter Walk Test
- Vital signs (SBP, DBP, HR)
- ECG
- Clinical laboratory tests including hematology, chemistry (with HbA1c) and urinalysis ([Section 6.6](#))
- Prostate-specific Antigen (PSA) test, males only
- Pre-fracture PADLs/IADLs
- Schedule the Baseline DXA scan.

Subjects who fulfill all inclusion and exclusion criteria will be randomized within 9 days of

Screening.

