9.3 Efficacy Analysis

9.3.1 DXA Scan Measurements

The total body less head and total lean body mass, hip bone mineral density, total body weight and fat mass, appendicular lean body mass and bone turnover markers will be analyzed using an Analysis of Covariance model with baseline value as a covariate and treatment as a primary factor.

Observed values, percentage change and absolute change from baseline and placebo adjusted change from baseline will be summarized using mean, standard deviation, coefficient of variation (CV%), median, minimum and maximum. A 95% confidence interval on the placebo adjusted change from baseline will also be presented.

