2.13. Analysis of Subgroups

There are no subgroup analyses planned for this study, but there is a plan to perform analyses to test for significant factor effects.

At the 3 month and 6 month analyses, we will test for a significant sex effect. Sex will be added as a factor into the ANCOVA models with least squares means and 95% confidence intervals being presented by treatment and sex. P-Values will be presented for the sex effect, treatment effect and sex*treatment interaction.

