2.15. Randomization Scheme and Codes

The randomization details are documented in a separate randomization plan.

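### Adding sex as a main effect to the primary and lean-mass ANCOVAs would be a cheap improvement: it costs one degree of freedom and may tighten the dose-placebo comparisons

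*SAP*

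**What the plan says.** - **Primary model.** SAP 2.10.1 fits an ANCOVA to absolute and percentage change at Month 3 "with baseline value as a covariate and treatment and region (country) as factors". SAP 2.10.2.1 gives the same terms for total and appendicular lean mass. Protocol 9.3.1 is shorter still, "with baseline value as a covariate and treatment as a primary factor". Sex is in none of these models, and no reason is given.
- **Availability.** Protocol 7.1 lists sex among the demographic data taken at Screening, so it is known for every subject before randomization.
- **Where sex is used.** SAP 2.13 says "Sex will be added as a factor into the ANCOVA models with least squares means and 95% confidence intervals being presented by treatment and sex", and then "P-Values will be presented for the sex effect, treatment effect and sex*treatment interaction". The SAP's table list includes Sex Effect tables for the primary endpoint, under both valid-DXA definitions and in both the ITT and Per Protocol populations.
- **Randomization.** SAP 2.15 says only "The randomization details are documented in a separate randomization plan". Whether sex was a stratification factor cannot be seen.
- **Size.** SAP 2.14 gives 26 per arm for 80% power at 0.5 mg, then sets a target of 104 randomized and about 23 completers per arm.

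**The concern.** The trial enrols men and women together and tests a drug that acts on the androgen receptor. Sex is the only factor that the SAP singles out for testing. If sex predicts change in lean mass beyond what baseline lean mass already explains, leaving it out makes the residual variance, and so the confidence intervals, larger than they need be. That matters most for the 0.5 mg comparison, where the completer target is below the SAP's own number for 80% power.

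The 2.13 model does not fill the gap. On its natural reading it contains the interaction, reports means by treatment and sex, and names no overall sex-adjusted placebo difference.

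**Working it through.** **1. Reproduce the SAP's power figures.** Inputs from SAP 2.14. Two-sided 5% is assumed, in line with "A 95% confidence interval on the placebo adjusted change from baseline will also be presented".

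- Pre-study: 30 per arm, difference 1.0 kg, SD 1.3. The normal approximation gives 84.6% and the noncentral t gives 83.4%, against 84% stated. For 1.5 kg the results are 99.4% and 99.3%, against 99% stated.
- Revised: differences 1.6, 2.4 and 4.1, SD 2.0 (units not stated). The smallest n per arm by two-sided t-test is 26, 16 and 7, as stated.

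The SAP's arithmetic is sound, and nothing below rests on an error in it.

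**2. Starting point at the reduced target.** With 23 per arm, difference 1.6 and SD 2.0, a two-arm t-test has 75.6% power. With the error term pooled over four arms, df = 92 - 4 - 1 = 87, SE = 2.0 x sqrt(2/23) = 0.590 and power is 76.5%. Country is left out because the number of countries is not stated; up to 3 country df change power by less than 0.1 point. The SD of 2.0 is treated as the residual SD after baseline.

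**3. Add sex.** Let R2 be the partial R-squared of sex given treatment and baseline. Then:

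- SE multiplier = sqrt((1 - R2) x (1 + 1/85)), where 85 = 87 - 2
- error df = 86

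The documents give no value for R2, so a range is assumed.

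| Partial R2 (assumed) | SE multiplier | Power, 0.5 mg vs placebo |
|---|---|---|
| model without sex | 1 | 76.5% |
| 0 | 1.006 | 76.0% |
| 0.02 | 0.996 | 76.9% |
| 0.05 | 0.980 | 78.1% |
| 0.10 | 0.954 | 80.3% |
| 0.15 | 0.927 | 82.4% |

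Break-even for the SE: 1 - 1/(1 + 1/85) = 1/86, a partial R-squared between 0.011 and 0.012.

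**4. Can the 2.13 model stand in?** If its overall treatment contrast weights men and women equally (SAP 2.20 specifies SAS defaults), its variance is multiplied by 1/(4pq), where p and q are the shares of the two sexes. The split is not in the documents.

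- Assumed 70/30: 1/(4 x 0.7 x 0.3) = 1.190, so the SE is multiplied by 1.091. Power is about 69% if sex explains nothing and about 74% at R2 = 0.10.
- Assumed 75/25: 1/(4 x 0.75 x 0.25) = 1.333, so the SE is multiplied by 1.155. Power is about 64% and 69% respectively.
- At 50/50 there is no penalty.

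**5. Chance imbalance is the same gain.** For a residual sex difference D, chance imbalance between two unstratified arms of n adds D² x 2pq/n to the variance of the treatment difference. That variance is 2 x SD²/n in total, so the added share is D² x pq/SD², which is the R2 of step 3. For illustration, with 30% of one sex, D = sqrt(R2) x 2.0/sqrt(0.21), which is 0.98 at R2 = 0.05 and 1.38 at 0.10. A 20-point imbalance would then shift the estimate by 0.20 or 0.28. Under simple randomization at 23 per arm, two arms differ by 20 points or more with probability 12% to 18% (one sex at 25% to 50%).

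**The case against.** The case against is that this is a preference between valid models, with an unproven gain. Most of its points stand.

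- **No error.** Leaving a baseline covariate out of a randomized comparison gives no bias and no excess type I error. A reader might infer that the primary result is compromised; the documents do not support that.
- **Not free.** A reader might infer that any prognostic value in sex is pure gain. It is not, because below the break-even value the SE rises. In a simulation of 4,000 trials per scenario (23 per arm, 30% of one sex, sex-baseline correlation 0.7, country not simulated), the sex-adjusted SE was the larger one in 78% of trials at R2 = 0, 49% at 0.02, 24% at 0.05 and 6% at 0.10.
- **Baseline may already carry it.** The model adjusts for baseline lean mass, and the primary endpoint is a percentage of baseline. Both may absorb much of any sex difference, so the residual R2 could be near zero.
- **Imbalance is not a second benefit.** Step 5 shows that it is the precision gain seen conditionally. It is also smaller if randomization was stratified by sex, which SAP 2.15 leaves unseen. Large shifts need large sex effects: with 75% of one sex and SD 2.0, a 3-point sex difference implies R2 = 0.1875 x 9/4 = 0.42, well above the range used here.
- **Sex is already examined.** SAP 2.13 will show whether sex matters. It plans a test and does not say that an effect is expected.

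These points limit the claim but do not remove the case for the change. The most that adding sex can be expected to cost is about 0.6% of the SE, while the gain is about 2% to 5% at R2 of 0.05 to 0.10. If sex was a stratification factor, that is a further reason to have it in the model.

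**Conclusion.** A cheap improvement to an acceptable model. The primary and lean-mass ANCOVAs leave out a pre-randomization variable that is known for every subject, and no planned analysis gives a main-effects, sex-adjusted placebo difference. Adding it moves power for 0.5 mg from 76.5% to between 76.0% and 82.4% over an assumed partial R-squared of 0 to 0.15. At about 0.10 it would bring 23 per arm back to roughly the 80% that the SAP associates with 26. For 1.0 mg and 2.0 mg, power at 23 per arm is already about 98% or more under the SAP's revised assumptions, so there the gain would be in interval width only.

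This rests on two-sided 5%, the SAP's revised effect and SD, 23 completers per arm and the assumed R-squared range. The documents do not show where in that range the trial lies.

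**What to change.** Before any unblinding, including the partly unblinded primary analysis of SAP 2.11:

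1. In SAP 2.10.1, and for the lean-mass endpoints in 2.10.2.1, add sex as a main effect next to baseline, treatment and country.
2. Keep the SAP 2.13 model for the interaction p-value and the by-sex least squares means.
3. State in SAP 2.15 whether randomization was stratified by sex.

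If the sponsor prefers to leave the primary model alone, pre-specify a sensitivity ANCOVA with sex and no interaction. The cost is one model term and one degree of freedom, with an SE expected to be at most about 0.6% larger if sex explains nothing further. No new data are needed. The SAP model already differs from Protocol 9.3.1 by including country, so the added term should be recorded with that change.
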